4.2 Outcome

The primary outcome is the proportion of patients with a 10 point change in the EORTC QLQ C30 quality of life questionnaire (with the BN-20 brain and ELD14 elderly patient subsets of questions added) from baseline to 8 weeks.

The impact of side effects from cranial radiotherapy will also be assessed by the secondary outcomes of

- MOCA cognitive screening questionnaire
- use of corticosteroids
- degree of grade 3-5 CTCAE toxicity
- overall and progression free survival

5 STUDY DESIGN and METHODS of DATA COLLECTION AND DATA ANALYSIS

The BRITER study is an observational cohort study. Eligible patients will be identified during the multidisciplinary team meeting by the participants' usual care team. They will have previously been informed of their diagnosis and then will meet a member of the oncology team to discuss treatment options. Once it has been decided with them by their usual care team that they are to have radiotherapy treatment, they will be given a PIS. After the patient has had sufficient time to read the PIS and have any questions answered by a member of the study team they will be asked to complete a consent form. They will also undergo the baseline clinical assessments prior to starting any

radiotherapy treatment. This will be done during the outpatient appointment with the neuro oncology team.

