The participant's treatment plan is not affected by enrolment in the study. The participant will then complete their radiotherapy treatment as planned. When they attend for their routine 4 week post-treatment follow up to the NHS neuro-oncology clinic they will repeat the EORTC-QLQ-C30 quality of life questionnaires and MOCA questionnaire as well as having assessment of their CTCAE radiotherapy toxicity score and steroid use. Again the EORTC-QLQ-C30 quality of life questionnaires could be sent to the patient in advance to complete prior to the clinic appointment or taken home and posted back. If the patient is unable to come to a clinic appointment during the required time frame they can be posted a questionnaire and send it back. The questionnaires should be completed within 3 to 5 weeks after treatment has finished. These will be recorded in the CRFs. Members of the study team are permitted to phone the patient to remind them to complete the questionnaires if they are not returned or can complete them over the phone with the patient. This would normally be done by the CNS or doctor who the patient will already know as part of their usual care team and would be accustomed to speaking to on the phone.

When participants attend for their routine 8 week (plus or minus 1 week) post-treatment follow up to the NHS neuro-oncology clinic they will repeat the same questionnaires and toxicity assessment. At this point their participation in the study is complete.

At the end of the study the results of the questionnaires from the CRFs will be transcribed into a database using Microsoft Excel. The CRFs will not contain the patient's name or recognisable patient details and the database will therefore be pseudo anonymised. A score of 24 or less on MOCA will be deemed abnormal. A change in baseline of 10 points or more on the EORTC-QLQ-C30 quality of life questionnaires will be deemed significant.

The MRI scans for the participants will be anonymised using the patient study ID and electronically transferred to [name], neuroradiologist The Walton Centre in Liverpool, for analysis. The following MRI sequences are ideally required:

- Axial T2 4mm slice thickness
- Volumetric T1 pre contrast (1mm or below)
- Post contrast volumetric T1 (1mm or below)
- DWI/ADC (4 mm slice thickness)
- Susceptibility weighted imaging (acquired volumetrically typically in the region of 1.5mm slice thickness but will vary with scanner setup)

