8.9 Study & safety assessments

As the study does not employ an Investigational Medicinal Product, Adverse Events (AE) or Serious Adverse Events (SAE) will be recorded and reported as per Sponsor's guidelines (Brighton & Sussex University Hospitals NHS Trust) and Health Research Authority (HRA) (see Figure 2 below).

A serious adverse event (SAE) is defined as an untoward occurrence that:

- (a) *results in death;*
- (b) *is life-threatening;*
- (c) *requires hospitalisation or prolongation of existing hospitalisation;*
- (d) *results in persistent or significant disability or incapacity;*
- (e) *consists of a congenital anomaly or birth defect; or*
- (f) *is otherwise considered medically significant by the investigator*

An SAE occurring to a research participant will be reported to the main REC where in the opinion of the Chief Investigator the event was:

- Related – that is, it resulted from administration of any of the research procedures, and
- Unexpected – that is, the type of event is not listed in the protocol as an expected occurrence.

	Who	When	How	To whom
SAE	Chief Investigator (CI) or sponsor	Within 7-14 days of the CI becoming aware of the event (in line with the Sponsor's Collaboration Agreement)	SAE report form for non-CTIMPs available from HTA website	Main REC for the trial
Urgent safety measures	Chief Investigator (CI) or sponsor Or exceptionally by local principal investigator (PI)	(i) Immediately (ii) Within 3 days	(i) By telephone (ii) Notice in writing setting out the reasons for urgent safety measures and the plan for further action	Main REC for trial REC co-ordinator will acknowledge within 30days If notified by PI, relevant local REC should also be informed

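### Grade 3-5 CTCAE toxicity is graded only at two attended clinics, so deaths and toxicity in patients too ill to attend have no scheduled route into the outcome

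*Combined protocol and SAP*

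**What the plan says.** Section 4.2 names "degree of grade 3-5 CTCAE toxicity" among the secondary outcomes. It gives no time window, worst-grade rule, attribution rule or denominator.

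Section 5 sets the timing. At the routine clinic 4 weeks after treatment, patients repeat the questionnaires as well as "having assessment of their CTCAE radiotherapy toxicity score and steroid use". At the 8-week clinic "they will repeat the same questionnaires and toxicity assessment", and then "At this point their participation in the study is complete". No CTCAE grading is listed at baseline or during radiotherapy.

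Section 5 also provides for missed visits. Patients "unable to come to a clinic appointment during the required time frame they can be posted a questionnaire and send it back", and staff "can complete them over the phone with the patient". In both places the object is the questionnaires; the toxicity assessment is named separately from them.

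Other parts of the protocol collect related information. Section 8.9 has AEs and SAEs recorded under the sponsor's guidelines, with an SAE definition that includes death and any event that "requires hospitalisation or prolongation of existing hospitalisation". Section 8.6 collects survival data at the end of the study. Section 7.3.2 obtains consent to access clinical records, but withdraws participants who lose capacity and bars further data collection from them. None of these sections mentions the CTCAE outcome.

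**The concern.** The outcome spans grades 3 to 5, and grade 5 is death. A death cannot be graded at a visit the patient attends, so the only scheduled assessment cannot observe the top category. Severe non-fatal toxicity has a similar difficulty, because it is a reason for missing clinic.

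This may not be a small group. Section 2 gives an average life expectancy of 3-6 months. Section 1 lists cognitive defects among the short-term effects of radiotherapy, so toxicity may itself lead to loss of capacity and withdrawal.

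At stake are the toxicity rate the study will report and the exploratory analysis of that rate against the five MRI scores. With no rule, sites could also treat the same death or missed visit differently.

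**Working it through.** The documents state no toxicity rate, non-attendance rate or power for this outcome, so there is no planned figure to reproduce. The check is an illustration on declared assumptions.

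**Inputs**
- Share not assessed, m = 20%. This borrows the attrition figure in Section 7.2.1, which is for questionnaires. Those have a post and telephone fallback and CTCAE has none, so its use here is an assumption.
- Grade 3-5 rate in attenders, pA = 15% (assumed).
- Grade 3-5 rate in non-attenders, pN = 40% to 60% (assumed).

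**Rate**
- True rate = (1 - m) × pA + m × pN.
- pN = 40%: 0.8 × 0.15 + 0.2 × 0.40 = 0.12 + 0.08 = 20%.
- pN = 60%: 0.8 × 0.15 + 0.2 × 0.60 = 0.12 + 0.12 = 24%.
- Recorded rate if only assessed patients are counted: 15%.
- Relative understatement: (0.20 - 0.15)/0.20 = 25%, and (0.24 - 0.15)/0.24 = 37.5%.

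These percentages describe the rate. The share of events that go unobserved is a different quantity: 0.08/0.20 = 40% and 0.12/0.24 = 50%. With 100 patients, 80 × 0.15 = 12 events are seen, out of 20 to 24.

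**Sensitivity**

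The bias is -m × (pN - pA) if only assessed patients are counted, and -m × pN if unassessed patients are counted as event-free. With an assumed pA of 20%:

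| Not assessed | pN relative to pA | Assessed only | Counted as event-free |
|---|---|---|---|
| 20% | equal | 0 points | -4 points |
| 20% | double | -4 points | -8 points |
| 20% | triple | -8 points | -12 points |
| 40% | double | -8 points | -16 points |

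**How many might not be assessed because of death**

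Assume exponential survival from the start of radiotherapy, a median of 3-6 months and a course of 2-6 weeks. The share dead by a visit is 1 - 0.5^(t/median), with t = (course weeks + weeks after)/4.345 months.
- 4-week visit: 14.7% (6-month median, 2-week course) to 41.2% (3-month median, 6-week course).
- 8-week visit: 23.3% to 52.5%.
- With a 12-month median: 7.7-12.4% and 12.4-17.0%.

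Patients chosen for radiotherapy may live longer than the average, and some who die before week 8 will have a week-4 grade. The 20% above is therefore neither a floor nor a ceiling.

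**Association with the MRI scores**

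If being unassessed depends only on toxicity, the odds ratio from a logistic model of assessed patients is not biased by it, although events and precision are lost. If it depends on both toxicity and the MRI scores, the odds ratio can move either way.

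**The case against.** The strongest reply is that the information is not lost. SAEs, including deaths and hospital admissions, are recorded; survival is itself a secondary outcome; consent covers clinical records; and the study team is the usual care team. A reader might infer from the visit schedule that grade 5 events cannot be recorded at all, and the documents do not support that. What stands is narrower: no rule takes these sources into the toxicity outcome. Survival data show that a patient died, not whether radiotherapy contributed. SAE reporting to the ethics committee concerns events arising from research procedures, whereas the radiotherapy here is usual care. No section says toxicity will be abstracted from records.

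A second reply is that the direction of bias is put in by assuming 40-60% against 15%. That is fair. A reader might infer a proven downward bias, but it needs either more toxicity in non-attenders or their being counted as event-free, and the documents settle neither. Non-attendance may reflect tumour progression. With no baseline CTCAE grade, tumour symptoms scored as toxicity could push the rate up. Nor do the documents say whether a visit grade is the current one or the worst so far, so loss of earlier toxicity among attenders cannot be assumed.

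Finally, Section 5 calls the secondary analyses exploratory and unpowered. That limits the weight of the point but does not remove it.

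**Conclusion.** The point holds as a gap in ascertainment. As written, the toxicity outcome depends on attendance at two clinics, and deaths and toxicity in patients too ill to attend have no scheduled route into it although they are recorded elsewhere.

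On the assumed rates the recorded figure understates the true rate by 25-37.5% in relative terms; other assumptions give anything from no bias upwards. A reader might also infer that the MRI-toxicity association would be attenuated. The documents do not support a fixed direction, only a loss of events and precision.

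The primary outcome and sample size are unaffected. The change should be made but is not critical to the study.

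**What to change.** - Define the outcome as the worst CTCAE grade from the start of radiotherapy to 8 weeks after it.
- For patients who die or do not attend, grade from telephone contact, clinical records and SAE reports.
- State an attribution rule for when a death counts as grade 5, separating radiotherapy from tumour.
- State the denominator, and report how many patients were not assessed and why.
- For patients withdrawn for loss of capacity, use only data collected before withdrawal, as Section 7.3.2 requires.

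The means largely exist: the team already telephones patients about questionnaires, and consent covers records. The cost is case report form wording and a limited record review. The downside is that record-based grades are somewhat less complete than clinic grades, so the source of each grade should be recorded.

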The majority of GBM patients over 65 who are actively treated by oncologists receive some form of radiotherapy to the brain. Short term side effects from radiotherapy include fatigue, headache, cognitive defects, nausea, weakness and a need for increased steroid doses. Longer term side effects include persistent cognitive defects, long term fatigue and hormonal imbalances^{ix}. Radiation causes an inflammatory response within the brain tissue as well as disrupting the blood brain barrier. It affects the vasculature of the brain with endothelial cell damage leading to microvascular dilatation, thickening of the vessel wall and increased risk of microbleeds and ischemic strokes in the months to follow^x. There is a risk of inducing tissue necrosis from occlusion of small blood vessels within the brain parenchyma, leading to coagulation, focal necrosis and demyelination. Animal models have suggested radiation is cytotoxic to developing neuroglial progenitor cells with areas of stem cells such as the hippocampus and periventricular zones, particularly vulnerable to damage, leading to longer term neurocognitive decline^{xixii}. There is evidence to suggest that radiotherapy can stabilise or improve functional ability for some older patients with GBM aswell as providing a survival advantage however

clinical experience shows that the degree of side effects experienced and their impact on quality of life varies widely within this patient cohort.

Risk factors for toxicities from radiotherapy include dose, fractionation and age however we have no more accurate ways of predicting which patients are more likely to suffer side effects. MRI has been shown to accurately pick up microhaemorrhages and other ischemic changes which may correlate with a 'vulnerable' brain pre-treatment^{xiiixiv}. These MRI changes have been examined in Alzheimer and dementia research with correlations shown between MRI markers and disease severity^{xv}, however they have not yet been used within the neuro oncology setting.

We aim to examine the relationship between MRI markers of a 'vulnerable' brain and degree of acute side effects and change in quality of life amongst a population of older patients being treated with cranial radiotherapy for GBM.

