Baseline clinical assessment of the patients will be conducted in the NHS neuro-oncology outpatient clinic setting. These will involve the EORTC-QLQ-C30 quality of life questionnaire with the BN-20 brain and ELD14 elderly patient subsets of questions added, the MOCA questionnaire (please see Appendix for examples of these questionnaires) and a record of the amount of corticosteroid the patient is currently taking. The EORTC-QLQ-C30 quality of life questionnaires are designed to be completed by the patient (they are allowed to ask for help completing from family/carer) and could therefore be taken home by the patient or completed in the waiting room rather than being completed within the clinic. There is a risk of the questionnaires not being filled in and posted back if participants forget. We have costed for stamped addressed envelopes to be given to the patients in order to post the questionnaires back. The study team (who know the participant and would usually speak to them on the phone anyway during their treatment pathway) are able to call the participant to remind them to post back the questionnaires. The MOCA is administered by a member of the study team.

The original copies of these questionnaires will be in the CRF, alongside details of the participant's age, gender, comorbidities, treatment plan and social situation which will be recorded by the study team.

In most cases, the participant will have undergone an MRI scan as part of their usual care plan prior to attending the neuro-oncology clinic. If this scan has the required imaging sequences needed for the BRITER protocol then no further scanning is required. This will be assessed by the neuro oncology consultant during the outpatient clinic appointment or a member of the study team prior to the appointment. A list of the required sequences will be readily available for the study team during this process. If not all of the required sequences were completed then the patient will undergo a further MRI scan. This will be done prior to the participant starting radiotherapy treatment but should not delay the start of their radiotherapy treatment. Depending on local guidelines, this scan will either take place on the same site or may require travel to another site. Travel costs will be covered for the patient and carer to attend the extra MRI scan.

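### CTCAE is graded only after radiotherapy and without an attribution rule, so grade 3-4 deficits present before treatment may be counted as radiotherapy toxicity

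*Combined protocol and SAP*

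**What the plan says.** Section 5 describes the baseline clinic assessments: "These will involve the EORTC-QLQ-C30 quality of life questionnaire with the BN-20 brain and ELD14 elderly patient subsets of questions added, the MOCA questionnaire", "and a record of the amount of corticosteroid the patient is currently taking". The CRF holds these "alongside details of the participant's age, gender, comorbidities, treatment plan and social situation". CTCAE is in neither list.

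At the 4-week post-treatment visit patients repeat the questionnaires "as well as having assessment of their CTCAE radiotherapy toxicity score and steroid use". At 8 weeks, plus or minus one week, "they will repeat the same questionnaires and toxicity assessment".

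Section 4.2 lists "degree of grade 3-5 CTCAE toxicity" among the secondary outcomes and introduces that list with "The impact of side effects from cranial radiotherapy will also be assessed by the secondary outcomes of". The outcome is not written as a change from baseline. Section 5 then relates the grade 3-5 score to five MRI scores, one of which is tumour volume. It calls the analyses of secondary endpoints exploratory and says the study is not powered for them.

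**The concern.** Quality of life, MOCA and steroid use are all measured before and after radiotherapy. CTCAE is the only repeated clinical assessment with no pre-treatment value.

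The Background says "Short term side effects from radiotherapy include fatigue, headache, cognitive defects, nausea, weakness and a need for increased steroid doses". Several of these, such as headache, weakness and cognitive deficit, can also come from a newly diagnosed glioblastoma. That is a clinical inference, not a statement in the protocol, but a modest one. Section 7.1.1 also admits patients whose physical impairments stop them completing the forms themselves, so some deficit at entry is expected.

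A grade 3 weakness seen at week 4 could therefore be new, worsened or unchanged, and the planned CTCAE data cannot show which. The error need not be random. If larger tumours cause more deficit before treatment and those deficits are recorded as toxicity, tumour volume will be associated with the outcome for a reason unrelated to radiotherapy. Section 3 hopes the results will identify patients better served without radiotherapy, so a false association would matter.

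**Working it through.** **Step 1: what is collected and when (Section 5).**

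| Measure | Baseline | 4 weeks | 8 weeks |
|---|---|---|---|
| QLQ-C30 with BN-20 and ELD14 | yes | yes | yes |
| MOCA | yes | yes | yes |
| Corticosteroid use | yes | yes | not named separately |
| CTCAE | no | yes | yes |

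No section gives an attribution rule or limits the outcome to new or worsened events. No section says that old deficits are to be counted, either.

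**Step 2: possible size.** The documents state no grade 3-5 rate, so there is no figure of the plan to reproduce. All inputs below are assumptions:

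- p, the proportion with a grade 3+ deficit before treatment: 5% to 20%
- persistence of that deficit to follow-up: 80%
- i, new grade 3+ toxicity among the remaining patients: 10% to 15%
- m, the share of persisting old deficits recorded as radiotherapy toxicity: 0 to 1

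Share of recorded events that predate treatment = 0.8·p·m / (0.8·p·m + (1 − p)·i)

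With m = 1 (every persisting deficit recorded):

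- p = 5%, i = 15%: 0.04 / (0.04 + 0.1425) = 22%
- p = 10%, i = 15%: 0.08 / (0.08 + 0.135) = 37%
- p = 20%, i = 15%: 0.16 / (0.16 + 0.12) = 57%
- p = 20%, i = 10%: 0.16 / (0.16 + 0.08) = 67%

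With m = 0.5, the two extremes become 0.02 / (0.02 + 0.1425) = 12% and 0.08 / (0.08 + 0.08) = 50%. With m = 0 the share is 0% throughout.

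**Step 3: cross-check with a second model.** Let new toxicity t (10% or 20%) be independent of a pre-existing deficit b (5% to 20%), with all deficits persisting. The observed rate is 1 − (1 − t)(1 − b·m). For the 73 patients that Section 7.2.1 expects at 8 weeks:

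- m = 0: no bias; 7.3 or 14.6 cases.
- m = 1, t = 10%: observed 14.5% to 28.0%, or 10.6 to 20.4 cases, of which 31% to 64% are not new toxicity.
- m = 1, t = 20%: observed 24.0% to 36.0%, or 17.5 to 26.3 cases, of which 17% to 44% are not new toxicity.

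In both models the result depends chiefly on m, which the plan does not fix.

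**The case against.** A reader might infer that old deficits will be counted, that 22-67% estimates the contamination, and that large tumours will appear to predict toxicity. The documents do not support any of these.

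- The measure is labelled a radiotherapy toxicity score and sits under side effects of cranial radiotherapy. Section 7.3.1 says the study team is the usual care team, which will often have seen the patient before treatment and can judge that a deficit is old. If it always does so, there is no bias.
- The 22-67% range needs every persisting deficit to be recorded as toxicity, and it rests on assumed rates. A higher rate of new toxicity lowers it: at p = 5% and i = 30%, 0.04 / (0.04 + 0.285) = 12%.
- Eligibility requires capacity, ability to communicate and fitness for radiotherapy, which limits severe deficit at entry. Grade 5 is death and cannot pre-exist, so only grades 3-4 are at issue.
- Some patients will have had debulking surgery, so tumour volume need not track existing deficit. The contralateral measures are less directly exposed to this route.
- BN-20, MOCA, steroid amount and comorbidities at baseline give some information on prior status, and consent covers access to clinical records.

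These points limit the size of the problem and its certainty. They do not close the gap. The study is multicentre with no written rule, so sites may judge differently. The baseline measures are not CTCAE grades and cannot show that a grade 3 finding is new.

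**Conclusion.** The omission is certain on the text: CTCAE has no baseline grade, and no rule separates old deficits from new toxicity. That old deficits enter the outcome is possible, not established. Under the assumed rates the pre-existing share of recorded events is 0% if assessors exclude them all and 22-67% if they record them all, with partial recording in between. A spurious association with tumour volume follows only if deficits are misattributed and also track volume.

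The damage is confined to an exploratory, unpowered secondary outcome. The primary outcome is a quality-of-life change measured from its own baseline and is unaffected. The change should still be made, because a contemporaneous grade that is not collected cannot be fully recovered later.

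**What to change.** 1. Grade the relevant CTCAE terms at the baseline clinic visit already planned in Section 5, and name them on the CRF.
2. In Section 4.2, define the secondary outcome as a grade 3-5 event that is new or worsened relative to baseline, term by term. A patient already at grade 3 for a term then counts only if that term worsens or another reaches grade 3-5.
3. State an attribution rule, applied by assessors without knowledge of the five MRI scores. The scores are produced remotely, so this is practicable, although the clinical team may have seen the scans themselves.
4. Grade any patients already enrolled from their clinical records, flag these grades as retrospective, and check whether the results change without them.

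The cost is one CRF page and a few minutes of clinician time at an existing visit. One limit remains: a baseline grade will not separate toxicity from later tumour progression, and the report should say so.

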2 RATIONALE

The poor prognosis of older GBM patients leads to an emphasis on the need for focusing on quality of life when deciding on treatment regimes. We have pathological markers which can help us determine sensitivity of the tumour to chemotherapy however we have no such guidance when it comes to making decisions about radiotherapy. If we were able to predict the degree of side effects likely to be experienced by a patient from radiotherapy treatment then it would enable us to make more individually tailored, patient centred treatment plans.

We aim to see if analysis of pre-radiotherapy MRI scans including T2 gradient echo and susceptibility weighted imaging sequences can correlate with acute treatment related toxicity and quality of life amongst patients aged 65 or over undergoing partial brain radiotherapy for GBM. As these patients have an average life expectancy of 3-6 months within the UK we are focussing on acute rather than long term side effects of radiotherapy.

MRI sequences will be utilised to determine any markers of background subclinical microvascular or degenerative disease in the normal brain including microhaemorrhage secondary to hypertension or cerebral amyloid angiopathy and atrophy with cortical volume measurement of the contralateral hemisphere. Additional susceptibility weighted sequences will be performed to identify the presence of microhaemorrhages in the contralateral normal-appearing brain parenchyma. These will be semi-quantitatively assessed using a modified established microhaemorrhage scoring methodology. Absolute measures of the contralateral normal-appearing hemisphere cortical volumes will be acquired using FSL freesurfer software and a volumetric T1 weighted acquisition. These techniques will give us a number of quantitative scores that can then be assessed for correlation with changes in quality of life and toxicity scoring systems.

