- 3D volumetric inversion recovery or MP-RAGE (additional sequence - to allow accurate quantification of cortical thickness/volumes using Freesurfer software in addition to scoring methods of atrophy, must be acquired at 1mm or below)
- Axial T2* gradient echo (4mm slice thickness)

The scan thickness and sequences performed may vary slightly between sites however prior to opening the sites will confirm they can produce the necessary sequences for [name] to produce 5 quantitative scores (tumour volume, contralateral hemispheric brain volume, contralateral cerebral hemisphere cortical thickness, microhaemorrhage score and white matter hyperintensity score) from the images which reflect the degree of potential vulnerability of the brain to the side effects of radiotherapy. These will then be analysed in relation to the clinical questionnaires, steroid usage and grade 3-5 CTCAE radiotherapy toxicity score using SPSS. Multivariable logistic regression models will be fitted to look for significant ($P<0.05$) relationships between the 10 point change in EORTC QLQ quality of life questionnaires and the MRI parameters. Exploratory statistical analysis of the relationships between the MRI parameters and the secondary endpoints will be performed although the study is not powered to detect statistically significant relationships between these.

The creation of the database and statistical analysis of the results will be performed by the CI with the help of a research assistant.

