7.2 Sampling

7.2.1 Size of sample

Sample size calculations have been performed assuming a clinically significant end point of a 10 point change (SD=22.1 taken from the EORTC website reference guide) in EORTC QLQ questionnaire score between baseline and 8 weeks. Estimated sample size for one-sample comparison of proportion to hypothesized value assuming a 2 sided alpha of 0.05 and power of 0.9 gives a sample of

73. However, allowing for 20% attrition in questionnaire completion, this results in a sample size of 91. With 73 patients at 8 weeks, we will have 90% power for 5% significance to detect 5% of patients achieving a 10 point change in QoL. However, this small a proportion will only allow us to fit one variable in the model. It has therefore been recommended by the statistical team to aim for a recruitment target of 100 patients in order to fit the 5 MRI variables to the model.

Patients who are enrolled within CTIMP studies will not be eligible to be recruited into the study as they would introduce too many unknown variables for adequate statistical analysis with a cohort of this size.

Previous work done by this study group has shown this is a feasible recruitment target over 2 years.

The study team will review recruitment at 9 months and if it has not reached 25% then they will explore ways to increase recruitment, including opening at other sites.

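### Cheap improvement: fit the five-score primary logistic model by Firth penalised likelihood, because ordinary maximum likelihood can fail if events are sparse and modestly inflates real effects otherwise

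*Combined protocol and SAP*

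**What the plan says.** Section 5 (Study design and methods) describes the primary model: "using SPSS. Multivariable logistic regression models will be fitted". The quoted run joins the end of one sentence to the start of the next. Relationships are to be judged at P<0.05. The predictors are "5 quantitative scores (tumour volume, contralateral hemispheric brain volume, contralateral cerebral hemisphere cortical thickness, microhaemorrhage score and white matter hyperintensity score"). Section 2 says of the microhaemorrhages: "These will be semi-quantitatively assessed using a modified established microhaemorrhage scoring methodology". No distribution is given for any score.

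The outcome is binary. Section 4.2: "The primary outcome is the proportion of patients with a 10 point change in the EORTC QLQ C30 quality of life questionnaire".

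Section 7.2.1 gives one event rate, for 73 patients reaching the 8-week assessment: "we will have 90% power for 5% significance to detect 5% of patients achieving a 10 point change in QoL". It then concedes that "this small a proportion will only allow us to fit one variable in the model", and the response is to "aim for a recruitment target of 100 patients in order to fit the 5 MRI variables to the model".

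Nothing in the document mentions penalised, exact or other small-sample estimation, or what will be done if the model does not converge.

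**The concern.** When events are few relative to the number of predictors, maximum-likelihood logistic regression has two weaknesses. The first is separation: some combination of scores divides events from non-events perfectly, an odds ratio runs to infinity and its Wald P-value means nothing. A strongly predictive score can then look non-significant, or be dropped after the fact to make the model converge. The second is small-sample bias away from the null when the true effect is not null.

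The primary result is a set of five odds ratios with P-values, and section 3 hopes that the scores will identify patients for whom other treatment options would be better. An estimator that behaves well across the range of possible event rates, fixed in advance, is therefore worth having if it is cheap.

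**Working it through.** **Inputs from the document.** Five scores (section 5); target 100, attrition 20%, 73 patients at 8 weeks, rate 5%, SD 22.1, two-sided alpha 0.05, power 0.90 (section 7.2.1). **Assumptions.** Maximum likelihood (ML) as the estimator; score distributions, correlations and effect sizes.

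**1. The plan's own figure.** One-sample proportion: n = [z₀.₉₇₅√(p₀q₀) + z₀.₉₀√(p₁q₁)]² / (p₁ − p₀)². The hypothesised value is not stated. With p₀ = 0.05 and p₁ = 0, n = 3.8415 × 0.0475 / 0.0025 = 72.99, so 73; then 73/0.80 = 91.25 (stated as 91). Other readings do not match: 0.05 against 0.10 gives 264, 0.05 against 0.15 gives 79, and a one-sample mean with 10/22.1 gives 52. So 73 is reproducible, but it concerns a single proportion and not the regression.

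**2. Events at the only stated rate.** Evaluable: 100 × 0.80 = 80. Events: 0.05 × 73 = 3.65; 0.05 × 80 = 4; 0.05 × 100 = 5 if nobody is lost. Per variable: 4/5 = 0.8 to 5/5 = 1.0. Going from 73 to 80 evaluable adds 0.05 × 7 = 0.35 of an event.

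**3. Other rates that could arise.** The document does not say whether a change means worsening or movement either way. If the SD of 22.1 applies to the change score (an assumption) and mean worsening is 0 to 10 points, the proportion worsening by at least 10 is Φ(−10/22.1) = 33% up to Φ(0) = 50%. Either direction gives 65% to 68%.

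**4. Simulation.** Model: logit P(event) = a + Σbⱼzⱼ, with a solved to give the target rate. There were 800 to 1,500 data sets per setting. Separation was checked by linear programming. Firth maximises log-likelihood + ½ log|information|. ML averages are over finite fits only.

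Mixed scores: three continuous, one binary present in about 20%, one four-level; underlying correlation 0.3; true OR 2 per SD on one continuous score (log OR 0.693). Data sets with no event count as having no finite estimate (expected 0.95⁸⁰ = 1.7% at 5%, n = 80).

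| n | Event rate | No finite ML estimate | Mean log OR, ML (÷ truth) | Mean log OR, Firth (÷ truth) |
|---|---|---|---|---|
| 80 | 5% | 41% | 0.95 (1.37) | 0.66 (0.95) |
| 100 | 5% | 31% | 0.82 (1.18) | 0.64 (0.92) |
| 80 | 10% | 11% | 0.81 (1.17) | 0.66 (0.95) |
| 80 | 30% | 0.1% | 0.79 (1.14) | 0.70 (1.01) |
| 80 | 65% | 0.9% | 0.79 (1.14) | 0.71 (1.02) |

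Across the mixed-score settings at 5% and n = 80, the share with no finite estimate was 31–48%. With all scores continuous it was 8–18% for null to moderate effects and 34% with five strong effects (OR 2 each). From a 20% rate upwards it was 1% or less in every setting.

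**5. Size of the remaining inflation.** With continuous scores at 30%, n = 80, correlation 0.5, ML averages 1.14 times the truth: 0.14 × 0.693 = 0.097 on the log scale, against an SD of 0.42, so 0.097/0.42 = 0.23 of an SD. Firth's SD there is 0.37, and 1 − 0.37/0.42 = 12% smaller. At n = 100, 30%, correlation 0.3, ML averages 1.08 times the truth.

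**6. Effect on the P<0.05 decision.** With no true effects, a 30% rate and n = 80, the ML Wald test rejected in 4.1–5.6% of data sets, score by score. At 32.5%, for a binary score present in 25% with true OR 2.5, power was 40% by the ML likelihood-ratio test and 37.5% by the Firth penalised likelihood-ratio test; another run gave 34% each for ML Wald and Firth. At a 5% rate, a strong predictor (OR 6) was detected in 21% of data sets by ML Wald and 33% by Firth, whose false-positive rate was 3–5%.

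**7. What Firth does not do.** At 5%, n = 80, true OR 2 on one continuous score and correlation 0.3, the 5th to 95th percentile of the Firth odds ratio runs from 0.74 to 5.5. Mean log OR at 5% was 0.88–0.97 times the truth in most settings, and 0.79 with five strong effects. Unmodified Firth also raised mean predicted risk above the observed rate by 2.4–2.7 points at 5%, 2.4 at 10%, 1.7 at 20% and 1.0 or less at 32.5%.

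**The case against.** The strongest reply is that the low-event case is not one the plan predicts. The 5% is the proportion the study could detect, and section 7.2.1 itself says it supports only one variable. If a third or more of patients meet the definition, ML does its job: separation is negligible, the error rate is near nominal and power is no worse than Firth's. This stands, and it limits the point. A reader might infer that the planned model will often fail at the trial's expected event rate; the document gives no expected rate, so that does not follow. Nor does the plan offer another rate that would rule the problem out.

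A reader might also infer that ML overstates the effect of MRI at any plausible rate. That is too strong. Inflation applies only to real effects, null odds ratios stay centred on 1, and at 20% or more the bias is small beside the sampling error.

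Third, Firth treats a symptom. With 4 events, fewer predictors or a continuous change outcome would address the cause, and a method that always returns a number could make an unsupportable model look sound. This stands too, and the fix must say so. Unmodified Firth also pulls predicted risks toward 0.5, which matters in a study about prediction, and needs an intercept correction.

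Finally, the sparse-score results need a sparse score. The document says only that microhaemorrhage is scored semi-quantitatively; that most patients would score zero cannot be read from it.

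**Conclusion.** The point holds as a cheap improvement, not as a fatal flaw. With about 80 evaluable patients and five scores, ML would be unreliable if events are as rare as 5%: no finite estimate in roughly 8–18% of data sets with continuous scores and null to moderate effects, and about 30–50% with a sparse score. At 20% or more, separation is 1% or less and P-values are essentially unchanged; what remains is about 5–15% inflation of non-null log odds ratios and a slightly larger spread than Firth's.

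This rests on reading unqualified logistic regression as ML, and on assumed score distributions, correlations and effect sizes. It does not show that Firth makes a five-variable model informative with 4–5 events; nothing does.

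**What to change.** In section 5, state that the five-score model will be fitted by Firth penalised-likelihood logistic regression, with penalised likelihood-ratio P-values and profile-likelihood 95% confidence intervals, in software that supports it. Add that any predicted risks will come from an intercept-corrected version (such as FLIC). Add that, if only 4–5 events occur, the five-variable estimates will be reported as too imprecise to interpret.

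The cost is two or three sentences and a package other than base SPSS; no extra patients or data are needed. The statistical downsides are slight shrinkage of estimates and, if the intercept correction is left out, predicted risks biased toward 0.5 (about 2–3 points at a 5% rate, about 1 point or less at 32.5%).
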